6.1. Study products

6.1.1. Description of the study products

6.1.1.1. Test product

Trade name: not assigned

International nonproprietary name: goflikicept

Product in-house code: RPH-104

Dosage form: solution for subcutaneous injections

Strength: 40 mg/mL

Doses: 80 mg and 160 mg

Dosing frequency: single

Route of administration: subcutaneous

Duration of treatment: single dose

Composition:

Component	Content in 1 mL	Relative content
Active ingredient		
RPH-104	40 (\pm 4) mg	-
Composition of buffer solution		
sucrose	60 mg	6%
polyethylene glycol (PEG) 3350	30 mg	3%
sodium chloride	2.92 mg	50 mmol/L
L-histidine	3.1 mg	20 mmol/L
pH 6.5		

Presentation: 4 mL transparent glass vials with rubber stopper, aluminum crimp cap and red lid. 1 vial contains 2 mL of study product solution 40 mg/mL.

Shelf life: 24 months. The expected maximum shelf life of the medicinal product is 3 years on the basis of the existing stability program.

Storage conditions: Protected from light at +2 to +8°C.

Manufacturer: Branch of R-Pharm, JSC "Yaroslavl Plant of Finished Dosage Forms", [name]

6.1.1.2. Placebo

Trade name: not applicable

International nonproprietary name: not applicable

Dosage form: solution for subcutaneous injections

Strength: not applicable

Dosing frequency: single

Route of administration: subcutaneous

Duration of treatment: single dose

Composition:

Component	Content in 1 mL	Relative content
Sodium chloride	9 mg	0.9%
water for injection	up to 1 mL	99.1%

Presentation: 4 mL transparent glass vials with a rubber stopper, aluminum crimp cap and red lid. 1 vial contains 2 mL of 0.9% sodium chloride solution (manufactured by JSC "R-Pharm", Russia) / plastic ampoules, 10 ml, 1 ampoule contains 10 ml of sodium chloride solution 10 ml (manufactured by the Hospira inc., USA).

Shelf life: 3 years.

Storage conditions: Protected from light at +2 to +8°C (manufactured by JSC R-Farm Russia) / at temperatures from +20 to + 25 ° C (manufactured by Hospira inc., USA).

Manufacturer: Branch of R-Pharm, JSC "Yaroslavl Plant of Finished Dosage Forms", [name] / Hospira incorporated, Lake Forest, USA.

6.1.1.3. Packing and labelling

Test product and placebo will be prepared and provided by Sponsor. Sponsor will provide the study sites with test product and placebo. Sponsor will be responsible for manufacturing, package and labelling of the products for the clinical study in accordance with the applicable local regulatory requirements.

6.1.2. Study product dosing scheme in treatment groups

To provide double blind study design, the study products will be administered as follows:

- in RPH-104 80 mg group, the subjects will receive 2 mL (80 mg) of RPH-104 and 2 mL of placebo on different administration sites;
- in RPH-104 160 mg group, the subjects will receive 2 mL (80 mg) of RPH-104 and 2 mL of (80 mg) of RPH-104 on different administration sites;
- in placebo group, the subjects will receive 2 mL of placebo and 2 mL of placebo on different administration sites.

6.1.3. Administration of the study product

Preparation of the study products will be made by unblinded study site personnel.

The study products will be administered by unblinded qualified study site personnel.

RPH-104/placebo will be administered subcutaneously at anterior abdominal wall at one of the areas shown in Figure 2. Each injection will be made to different sites with relevant records in eCRF.

[figure not shown]

Figure 2. Anterior abdominal wall sites for the study product administration

6.1.4. Treatment compliance

Given that administration of the study products will be performed by the study site personnel, evaluation of dosing regimen compliance is not planned.

6.1.5. Overdose management

No cases of RPH-104 overdose have been reported. The treatment of overdose cases is symptomatic.

6.2. Allowed and forbidden concomitant therapy

6.2.1. Allowed concomitant therapy.

6.2.1.1. General provisions

If concomitant pathology is not an exclusion criterion, the treatment of concomitant pathology during the study should be carried out according to the regular scheme. At that, concomitant therapy should not be forbidden by the Protocol (see section 6.2.2).

Concurrent/ongoing treatment with any cytochrome P450 substrate (see Table 3) with a narrow therapeutic index should be clinically monitored to ensure therapeutic effect is maintained; doses of the cytochrome P450 substrate may need to be adjusted as the enzyme may be normalized with co-administration with RPH-104.

Table 3. Examples of drugs that are P450 substrates

	Highly sensitive substrates	Moderately sensitive substrates
CYP1A2	alosetron, caffeine, duloxetine, melatonin, ramelteon, tasimelteon, tizanidine	clozapine, pirfenidone, ramosetron, theophylline
CYP2B6	bupropion ¹	efavirenz ¹
CYP2C8	repaglinide ²	montelukast, pioglitazone, rosiglitazone

CONFIDENTIAL

Translation dated 27-Oct-2021

based on Russian Version 4.0 dated 02-Oct-2021

Page 52 of 98

	Highly sensitive substrates	Moderately sensitive substrates
CYP2C9	celecoxib ³	glimepiride, phenytoin, tolbutamide, warfarin
CYP2C19	S-mephenytoin, omeprazole	diazepam, lansoprazole ⁴ , rabeprazole, voriconazole
CYP2D6	atomoxetine, desipramine, dextromethorphan, eliglustat ⁵ , nebivolol, nortriptyline, perphenazine, tolterodine, R-venlafaxine	encainide, imipramine, metoprolol, propafenone, propranolol, tramadol, trimipramine, S-venlafaxine
CYP3A	alfentanil, avanafil, buspirone, conivaptan, darifenacin, darunavir ⁶ , ebastine, everolimus, ibrutinib, lomitapide, lovastatin ⁷ , midazolam, naloxegol, nisoldipine, saquinavir ⁶ , simvastatin ⁷ , sirolimus, tacrolimus, tipranavir ⁶ , triazolam, vardenafil	alprazolam, aprepitant, atorvastatin ³ , colchicine, eliglustat ⁵ , pimozide, rilpivirin, rivaroxaban, tadalafil
	budesonide, dasatinib, dronedarone, eletriptan, eplerenone, felodipine, indinavir ⁶ , lurasidone, maraviroc, quetiapine, sildenafil, ticagrelor, tolvaptan	

1 Listed based on an in vivo induction study and the observed effect might be partly attributable to induction of other pathway(s).

2 OATP1B1 substrate.

3 Listed based on pharmacogenetic studies.

4 S-lansoprazole is a sensitive substrate in CYP2C19 extensive metabolizer subjects.

5 Sensitive substrate of CYP2D6 and moderate sensitive substrate of CYP3A.

6 Usually administered to patients in combination with ritonavir, a strong CYP3A inhibitor.

7 Acid form is an OATP1B1 substrate.

Abbreviations: CYP: cytochrome P450;OATP1B1: organic anion transporting polypeptide 1B1.

Source: <https://www.fda.gov/drugs/drug-interactions-labeling/drug-development-and-drug-interactions-table-substrates-inhibitors-and-inducers#table3-1>; accessed 30 Dec 2019.

Information on concomitant medicinal products (trade name, composition, dose or dose adjustment, indications, dosing frequency, method of administration, treatment initiation, treatment discontinuation) taken by the subject for 5 half-lives of the drug or 30 days (whichever is longer) prior to enrollment and during the study should be recorded in the relevant section of eCRF including screening visit. All subsequent changes in concomitant therapy during the study should also be reflected in eCRF.

6.2.1.2. Contraception

Throughout the clinical study female subjects with childbearing potential should use highly effective contraceptive methods including combination of two of the following methods (a+b or a+c or b+c):

- oral, injection or implanted hormonal contraceptives; in case of oral contraceptives, the female subjects should administer the same product for at least 3 months prior to the study therapy;
- intrauterine device or contraceptive system;

CONFIDENTIAL

Translation dated 27-Oct-2021

based on Russian Version 4.0 dated 02-Oct-2021

c) barrier methods: condom or occlusive cap (diaphragm or cervical cap/vaginal fornix cap) with spermicidal foam/gel/film/cream/vaginal suppository

The study may enroll females not using highly effective methods of contraception if they are diagnosed as sterile for the following reasons:

- history of hysterectomy, bilateral ovariectomy, bilateral tubal ligation;
- menopause (physiological amenorrhea with lack of menses within at least 2 years);

Prior to the study, female subjects of childbearing potential should be informed on the importance of contraception during the study and potential risk factors in case of unwanted pregnancy.

Subjects should sign ICF specifying this information. Pregnancy test will be performed by female subjects with childbearing potential.

6.2.2. Forbidden concomitant therapy

During the study, the following medicinal products will be forbidden in the terms specified:

- biological (except for RPH-104) including but not limited to: tocilizumab, rituximab, TNF α inhibitors [Visit 1 Day 1 - Visit 4 Day 28];
- immunosuppressants [Visit 1 Day 1 – Visit 4 Day 28] including but not limited to:
 - corticosteroids at doses of >1 mg/kg of methylprednisolone equivalent orally as well as systemic, except for intravenous (i.v.) ones for acute allergic reactions;
 - cyclosporine A, methotrexate etc.;
- colchicine [Visit 1 Day 1 – Visit 4 Day 28];
- anakinra, canakinumab, rilonacept [Visit 1 Day 1 – Visit 6 Month 12];
- immunization with live vaccines within 90 days prior to or after the study product administration;
- any experimental products.

NSAIDs are not forbidden.

6.2.3. Use of the medicinal products not allowed or not provided for by the Protocol

If a life- or health-threatening situation took place during the study and the subject required additional therapy with forbidden medicinal products or the medicinal products not specified in the Protocol, such medicinal products may be prescribed in this case. However, Study Sponsor should be notified on the Protocol deviation within 24 hours. In this case, the subject who received forbidden medicinal products or medicinal products not specified in the Protocol may be excluded from the study.

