4.3.2. Treatment period

The day of treatment initiation will coincide with the day of screening, treatment period will include single administration of the study products.

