5.4.2. Early withdrawal criteria

The subject may withdraw the study at any time before its termination (Visit 6). The investigator may also decide to withdraw a subject at his/her own discretion.

The reasons for study withdrawal will be reflected in source medical documents and eCRF and may include the following:

1. Recall of informed consent to participate in the study.
2. Serious or intolerable AE requiring withdrawal from the study at the investigator's discretion.
3. Investigator's decision that continuation of the study participation contradicts the subject's interests.
4. Investigator's decision if the subject does not follow the study procedures and/or Protocol.
5. Protocol deviation which, according to the investigator, requires early subject withdrawal from the study (e.g. necessity or performance of additional therapy forbidden by the Protocol). In this case, decision on the subject withdrawal will be agreed with Sponsor.
6. Study termination by Sponsor.
7. Study termination by regulatory authorities.
8. Pregnancy of the subject.
9. Death of the subject.

5.4.3. The list of data by early withdrawn subjects and terms of their collection

In case of early withdrawal, justification of such decision and its reason should be specified in source medical documents and eCRF.

Where a subject recalls his/her informed consent, the investigator should try to learn the cause of such a decision.

In case of early withdrawal at the follow-up period post dosing (Visit 1 Day 1 – Visit 4 Day 28) an early withdrawal visit is advised including Visit 4 procedures.

In case of early withdrawal during additional clinical follow-up period (Day 29 – Visit 6 Month 12) an early withdrawal visit is advised including Visit 6 procedures.

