5.4.4. Replacement of withdrawn subjects and accounting of their data

The subjects withdrawn will not be replaced.

CONFIDENTIAL

Translation dated 27-Oct-2021

based on Russian Version 4.0 dated 02-Oct-2021

The data of the subjects withdrawn before randomization will be taken into account in the study report in subject disposition analysis only. The data from the subjects withdrawn post randomization will be taken into account in the final analysis in the relevant set (see Section 9).

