5.4.5. Follow-up of withdrawn subjects

Follow-up of the subjects withdrawn due to a SAE will be performed until its resolution or stabilization.

The subjects withdrawn for other reasons will not be followed.

6. Treatment of the study subjects

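### Section 5.4.5 ends outcome follow-up at withdrawal, including after emergency use of a forbidden drug, although the only dose is on Day 1 and five secondary endpoints run to Day 365

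*Combined protocol and SAP*

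**What the plan says.** Section 5.4.5 sets two rules. For withdrawals caused by an SAE: "Follow-up of the subjects withdrawn due to a SAE will be performed until its resolution or stabilization". For everyone else: "The subjects withdrawn for other reasons will not be followed".

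One entry to these rules is emergency medication. Section 6.2.3 permits a forbidden or unlisted drug in a life- or health-threatening situation and treats its use as a deviation. It adds that "the subject who received forbidden medicinal products or medicinal products not specified in the Protocol may be excluded from the study". Section 5.4.2 item 5 gives the matching example of a deviation that can lead to withdrawal, "necessity or performance of additional therapy forbidden by the Protocol", with the safeguard "In this case, decision on the subject withdrawal will be agreed with Sponsor".

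On what is collected at exit, Section 5.4.3 says that for an exit up to Day 28 "an early withdrawal visit is advised including Visit 4 procedures"; a later exit has the Visit 6 procedures. Section 5.4.4 adds: "The data from the subjects withdrawn post randomization will be taken into account in the final analysis in the relevant set".

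On dosing, Section 4.3.2 says that the "treatment period will include single administration of the study products", on the day of screening. Secondary endpoints 4 to 8 (Section 7.1) count death, hospitalization and new heart failure from Day 1 to Day 365. Section 9.3.3.2 compares the proportions by Fisher's exact test.

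**The concern.** In a trial with continuing dosing, withdrawal at least stops further exposure. Here the whole dose is given on Day 1, so withdrawal only ends observation, and 12-month outcomes are what the late secondary endpoints need. No section separates leaving the study from leaving outcome follow-up, and none provides for outcome or vital status to Month 12 after an exit.

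The emergency-drug path deserves attention because its trigger is a life- or health-threatening event. Subjects who leave this way may have a different risk of later death or heart failure from those who stay, so the loss may be related to prognosis. What could be missed is a later, separate event between exit and Month 12. In the proportion of all FAS subjects, such a subject stays in the denominator and the unseen event counts as no event. The available text does not say how the valid percentage treats the subject, and Section 9.1 leaves analysis detail to the SAP.

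**Working it through.** **The plan's own power figure first.** Section 9.4 gives d = 0.80, two-sided alpha 0.05 and 34 per arm, and states power above 90%, and above 80% after 20% loss. A two-sample t-test (noncentral t) gives 90.2% at n = 34. With 20% loss, 34 × 0.8 = 27.2; n = 27 gives 82.2%. Both statements reproduce. They concern the 14-day hsCRP AUC, so only exits before the Day 14 sample could matter. Even two exits in an arm, 2/34 = 5.9%, lie well inside the 20% allowance.

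**Can an exit leave 12-month outcomes unobserved?**
- Coded as a protocol deviation: no follow-up (5.4.5).
- Coded as an SAE: follow-up to resolution or stabilization of that event only (5.4.5; 8.2.12 is similar for all AEs).
- The early withdrawal visit includes outcome registration (4.3.4.8), but it is a single contact at exit and cannot record later events.
- Section 8.2.4, on its wording, records SAEs for up to 30 days after study product discontinuation or to the last visit, whichever is later. With one dose on Day 1 that is about Day 1 + 30 = Day 31. Deaths and hospitalizations are SAEs (8.2.5), so these are covered to about then.

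None of these reaches Month 12.

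**How much time is lost.** An exit at Day 28 leaves 365 − 28 = 337 of 365 days (92.3%) unobserved, and more if the exit is earlier. On the 8.2.4 reading, about 365 − 31 = 334 days remain uncovered for deaths and hospitalizations. Visits 5 and 6 are lost, which is 2 of the 5 scheduled outcome registrations (Visits 2 to 6). Days are not events.

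**Size in the comparison.** One event is 1/34 = 2.9 percentage points of an arm. The documents give no number of such exits, so the following rests on assumptions: 0 to 2 exits per arm, each with a 10 to 30% risk of a later, separate event that goes unseen.

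Bias in the risk difference = (exits in A × risk in A − exits in B × risk in B) / 34.

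| Exits, A vs B | Bias, percentage points |
|---|---|
| 0 vs 0, or equal exits at equal risk | 0 |
| 1 vs 0 | 0.10/34 to 0.30/34 = 0.3 to 0.9 |
| 2 vs 0 | 0.20/34 to 0.60/34 = 0.6 to 1.8 |

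If instead exits are equal (k per arm), exited subjects carry their own arm's event risk and all their events are lost, a 10-point difference becomes 10 × (1 − k/34): 9.7 points for k = 1 and 9.4 for k = 2. That is mild attenuation.

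**The case against.** The case for leaving the text alone is substantial.

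- **The path is narrow.** Exclusion under 6.2.3 is optional. Item 5 of 5.4.2 requires the investigator to judge that withdrawal is needed, and the Sponsor to agree (also Section 10.4). In 6.2.2 the bans on biologics in general, immunosuppressants and colchicine end at Day 28, and intravenous corticosteroids for acute allergic reactions and NSAIDs are not forbidden. Anakinra, canakinumab and rilonacept are barred to Month 12, and experimental products have no stated end date, so late exits are possible but should be few. This stands.
- **Much is already captured.** A trigger that itself led to a new admission already counts for endpoint 5. A death from the triggering SAE should be recorded. This stands, but only for the trigger. A subject counted under endpoints 6 and 7 for heart failure without admission can still be missed for endpoint 8.
- **SAE reporting covers the rest.** Section 8.2.6 asks for SAE reports until the end of the study. But it obliges a site to report what it learns; it schedules no contact, and 5.4.5 says there is none. New heart failure managed without admission need not be an SAE.
- **The endpoints are secondary** in a study that calls itself exploratory (9.4, 9.5). This limits the severity.

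A reader might also infer three stronger things that the documents do not support. First, that 6.2.3 removes subjects from the FAS: Section 9.2 defines the FAS by dosing and one later hsCRP value, and 5.4.4 keeps data already collected. Second, that ordinary unlisted medication endangers a subject's place in the study: 6.2.1.1 allows usual treatment unless a drug is forbidden, so that wording is a minor point. Third, that the treatment comparison is biased: this needs exits or later risks to differ between arms in a way that distorts the difference, and the documents give no figures on either.

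**Conclusion.** The point holds as a weakness of Section 5.4.5, with 6.2.3 and 5.4.2 item 5 as one entry to it. The plan states a rule that can end observation of 12-month outcomes when withdrawal withholds no treatment, and on this path the loss may be related to prognosis. Nothing in the protocol secures outcomes to Month 12 after such an exit.

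The likely effect is zero to small. The one-sided scenarios give at most 1.8 percentage points, under assumed exits and risks; the actual number of exits is unknown and may be zero. The primary analysis and its power statement are not in question. This is an improvement the Sponsor could make, not a flaw that undermines the trial.

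**What to change.** **Main change, Section 5.4.5.** Replace "The subjects withdrawn for other reasons will not be followed" with: *For all withdrawn subjects, whatever the reason, outcome registration continues to Month 12 (by telephone if needed, as at Visit 5) unless consent is withdrawn or the study is terminated.* Keep the sentence on SAE follow-up. This also covers withdrawals for other reasons, such as investigator decision or non-compliance.

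**Optional, for consistency.** In 6.2.3, replace the permission to exclude with: *the use is recorded as a deviation and is not by itself a reason to end outcome follow-up (see 5.4.5).* In 5.4.2 item 5, drop the forbidden-therapy example. On its own that deletion changes little, because the general wording of item 5 would still permit withdrawal; the change to 5.4.5 does the work. The list of forbidden drugs and the other withdrawal reasons stay as they are.

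**Cost.** A short amendment; up to two extra contacts per withdrawn subject (Months 6 and 12); and possibly a consent-form line on contact after withdrawal. Telephone contact alone will not always suffice. The blinded outcome committee (9.8) classifies events by the Appendix 1 criteria, which for heart failure hospitalization require examination or laboratory findings and treatment details, so source records would have to be retrieved.

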6.3. Accounting of the study products

The products for the study will be provided by Sponsor to the study initiator with Acceptance act and certificate of analysis. The product delivery from Sponsor should be accepted and processed by a responsible person (Investigator or authorized person). All study product accounting and storage procedures will be made using specially appointed unblinded members of the investigator's team. The products will be stored until their dispensing in a dry, protected from light place: in the fridge (suitable for medicinal product storage) at temperature from +2 to +8°C for RPH-104 and placebo manufactured by JSC R-Pharm, and at a temperature from +20 to + 25 ° C - for placebo produced by Hospira inc., USA. The products will be stored in specially equipped limited access premises.

The study organizer will provide the study products to the study site in the amount sufficient for the study.

CONFIDENTIAL

Translation dated 27-Oct-2021

based on Russian Version 4.0 dated 02-Oct-2021

Page 54 of 98

Control, accounting and storage of the products in clinical center shall be made by the qualified person authorized by the principal investigator according to the internal regulations of the clinical center and Sponsor's instructions.

Unblinded investigators should assure the product storage in safe conditions preventing from loss, theft and impaired environmental conditions (temperature) outlined in Guidelines on medicinal product handling and Investigator's Brochure.

Administration of the study products will always be made at the study site by the appointed unblinded study team member.

More detailed information on acceptance, storage, accounting and administration to the study subjects is provided in Guidelines on medicinal product handling for investigators.

Study product accounting, storage and issue will also be monitored by unblinded monitor on behalf of Sponsor.

6.4. Control of compliance

Monitoring of compliance with all the study procedures will be made by the Principal Investigator.

7. Efficacy evaluation

7.1. List of efficacy parameters

Primary endpoint

1. hsCRP area under curve (AUC) from Day 1 (baseline) until Day 14 [Visit 1 Day 1 – Visit 3 Day 14].

Secondary endpoints

1. hsCRP area under curve (AUC) from Day 1 baseline) until Day 28 [Visit 1 Day 1 – Visit 4 Day 28].
2. BNP area under curve (AUC) from Day 1 (baseline) until Day 28 [Visit 1 Day 1 – Visit 4 Day 28].
3. NT-pro-BNP area under curve (AUC) from Day 1 (baseline) until Day 28 [Visit 1 Day 1 – Visit 4 Day 28].
4. Incidence of fatal outcomes (cardiac and non-cardiac) during 12-month follow-up period [Visit 1 Day 1 – Visit 6 Day 365].
5. Incidence of hospitalizations due to HF or other cardiac reasons not associated with HF, or due to non-cardiac reasons during 12-month follow-up period [Visit 1 Day 1 – Visit 6 Day 365].
6. Incidence of new cases of HF (defined as hospitalization due to HF or new onset of HF) during 12-month follow-up period [Visit 1 Day 1 – Visit 6 Day 365].
7. Incidence of “fatal outcome (due to any reason) or hospitalization due to HF or new onset of HF” Frequency of fatal outcomes for any cause OR hospitalization for HF OR the development of HF in the outpatient settingsduring 12-month follow-up period [Visit 1 Day 1 – Visit 6 Day 365].
8. Incidence of “fatal outcome (due to any reason) or hospitalization due to HF” during 12-month follow-up period [Visit 1 Day 1 – Visit 6 Day 365].

- 9. 9. Changes in levels of BNP and NT-pro-BNP during 12-month follow-up period compared to baseline [Visit 1 Day 1 – Visit 6 Day 365].
- 10. Changes in structural and functional echocardiographic parameters after 12 months compared to baseline [Visit 1 Day 1 – Visit 6 Day 365].

Exploratory endpoints

- 1. Changes in concomitant therapy [Visit 1 Day 1 – Visit 6 Day 365].
- 2. Interaction between STEMI outcomes and peculiarities of coronary bed lesion based on baseline CAG results [Visit 1 Day 1 – Visit 6 Day 365].

